**NCT05995977**

**Document Date: 1 August 2023**

## ABSTRACT

Hypertension is a major global public health problem. For success in the prevention and management of hypertension, it is necessary to ensure that patients receive timely and accurate diagnosis, acquire healthy lifestyle habits, start antihypertensive drug treatment on time, and ensure compliance with treatment. The study was conducted in a pre-test-post-test parallel group randomized controlled design in order to determine the effects of nursing interventions consisting of hypertension education and sending short messages, created by utilizing Rogers' Protective Motivation Theory (CMT), on medication compliance and healthy lifestyle behaviors for hypertensive individuals. The study was conducted at Family Health Center No. 7 in the center of Karaman province between November 2023 and May 2024. The study group included individuals between the ages of 40 and 59, who had low compliance with treatment, had no communication problems in terms of hearing, vision, and understanding, used a mobile phone to receive the short message to be sent by the researcher, and were diagnosed with primary hypertension. The study was conducted with 78 hypertensive individuals, 39 in the intervention group and 39 in the control group, calculated with 95% power. Ethics committee, institution, scale use permission and written consent of the participants were obtained before the study. Data were collected at the beginning ( $T_0$ ), at the end of the third month ( $T_1$ ) and at the end of the sixth month ( $T_2$ ) using the Personal Information Form, Antihypertensive Drug Treatment Adherence Scale, Healthy Lifestyle Behaviors Scale, Blood Pressure Monitoring Form. Multiple nursing interventions consisting of hypertension education, brochure and short message created by using Rogers' KMT were applied by the researcher for 14 weeks. The control group was expected to continue their routine treatment for six months and no intervention was applied. Pre-test, interim and post-test measurements were collected by the researcher using the face-to-face interview method. Blindness was applied in terms of statistics expert and reporting. In the analysis of data, t test, chi-square test (Pearson chi-square/Fisher exact test) were used in independent groups, mixed order analysis of variance (ANOVA) was used in comparing variables according to follow-up times in groups, and Bonferroni correction was used in comparing main effects in the analyses. After the applied nursing interventions, a significant difference was found between the total mean scores of Antihypertensive Drug Treatment Adherence Scale, Healthy Lifestyle Behaviors Scale and systolic blood pressure and diastolic blood pressure values of the intervention and control groups ( $p<0.05$ ). After the nursing interventions, the total mean scores of Antihypertensive Drug Treatment Adherence Scale and systolic blood pressure and diastolic blood pressure values of hypertensive

individuals in the intervention group were significantly lower compared to the control group, and the total scores of Healthy Lifestyle Behaviors Scale were significantly higher ( $p<0.05$ ). Based on the results of this study, feasible, economical interventions combining health education and technology can be recommended as an important tool in health services to reduce the burden of hypertension in society.

**Keywords:** Nursing, Hypertension, Medication adherence, Protective motivation theory, Healthy lifestyle behavior.

## **1. MATERIALS AND METHODS**

### **1.1. Type of Research**

This study was conducted in a randomized, pre-test, post-test controlled experimental parallel design. The research was reported according to CONSORT 2022 (Junqueira et al., 2023).

### **1.2. Location and Characteristics of the Research**

The research was conducted at Family Health Center No. 7 (ASM) affiliated with the Karaman Provincial Health Directorate. The center serves a total of 9,150 people. Three family physicians, three family health workers and one assistant staff work at this center. The ASM provides service between 08:30 and 17:30 on weekdays. The ASM has a laboratory, injection-dressing-emergency room and an examination room for patients. Polyclinic services are provided at all three polyclinics. Regarding hypertension, cardiovascular risk assessment, screening, follow-up and result procedures are performed for individuals registered in the family medicine unit for hypertension. In terms of the duties of the nurse, the nurse measures the blood pressure of hypertensive patients who apply to the center when deemed necessary and directed by the physician, and provides education and counseling services on the disease, medication use and health lifestyle behaviors. There is no planned education or telephone follow-up for patients with hypertension at the center.

### **1.3. Universe of the Research and Study Group**

**Universe:** The research population consists of 407 individuals with primary hypertension between the ages of 40-59, registered in Family Health Center No. 7.

**Working group:** In this study, the sample size was calculated before the data collection stage at a 95% confidence level using the "G. Power-3.1.9.2" program to determine the study group. Özpancar's (2013) study, which examined the effect of education given by nurses on

treatment compliance in patients with hypertension, was used for the calculation. According to the data obtained from the study in question, the sample number required for the study was determined as 35 for each group (35 people for the control group + 35 people for the experimental group; 70 people in total) by taking the alpha value of 0.05 for the Mann Whitney U test, the effect size of 0.90, and the theoretical power as 95%. The 10% loss rate in previous studies (Zahr et al., 2019; Dağıstan Aköz, 2022) was taken into account and it was decided to include a total of 78 participants, 39 in each group.

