#### 1.9.8. Measuring results

The primary outcomes of this study were the level of compliance with antihypertensive drug treatment and healthy lifestyle behaviors. Secondary outcomes were changes in SBP and DBP levels. Primary and secondary outcomes were assessed at the first month ( $T_0$ ), the end of the third month ( $T_1$ ), and the end of the sixth month ( $T_2$ ).

Preliminary application: After obtaining permissions for the study, 8 hypertensive individuals (10% of the sample) who met the inclusion criteria were provided with data collection tools and an evaluation of the clarity of the questions; no problems were encountered. These 8 individuals were excluded from the sample.

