**THE EFFECT OF NURSİNG INTERVENTİONS BASED ON CONSERVATİON
MOTİVATİON THEORY ON DRUG ADHERENCE AND HEALTHY LİFESTYLE
BEHAVİORS İN PATİENTS WİTH HYPERTENSİON: A RANDOMİZED
CONTROLLED STUDY**

NCT05995977

Document Date: 20 June 2024

Statistical Analysis Plan

In this study, data analysis was performed using the IBM SPSS Statistics Standard Concurrent User V 26 (IBM Corp., Armonk, New York, USA) program. Descriptive statistics were given as unit number (n), percentage (%), mean (X), standard deviation (SS), median (M), minimum (min) and maximum (max) values. Reliability for scales and their sub-dimensions was examined using Cronbach's Alpha coefficient. Scales with a Cronbach's Alpha coefficient above 0.60 were considered reliable. Skewness and kurtosis values were examined to test whether the data met the assumption of normality. In the decision stage, if the absolute skewness (Skewness) value is below ± 2.0 and the kurtosis value is below 7.0, it is decided that the data is normally distributed (Kim, 2013). Accordingly, the skewness and kurtosis values of the variables used in the study are given in Table 3.6 and it was found that the data were suitable for normal distribution. Independent sample t test was used to compare numerical descriptive characteristics of patients between groups, and chi-square tests (Pearson chi-square/Fisher exact test) were used to compare categorical descriptive characteristics between groups. Mixed order analysis of variance (ANOVA) was used to compare variables according to follow-up times in groups. Bonferroni correction was applied to compare main effects in the analyses. A p value of <0.05 was considered statistically significant.

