Intention to treat (ITT) analysis was performed in the evaluation of the data. ITT is a basic method used in maintaining randomization and preventing bias in case of withdrawal from the study. The approach to be applied when handling missing data varies according to whether the data is discrete or continuous. The most common method used in filling in missing data in continuous data is to fill in the last observed data by repeating the outcome measurements (Last Observation Carried Forward). Since it was not possible to reach 7 individuals who dropped out during the research process for the ITT analysis of this study, the post-tests were filled in by repeating the answers given by the patients in the pre-tests and the missing data were completed in this way. A summary of the statistics used in this study is shown in Table 1.

Table 1. Statistics used in the study (n=78).

Evaluated statistics	Statistical methods
Normal distribution	Skewness and kurtosis values
In comparing numerical descriptive characteristics between groups	Independent Sample t Test
In comparing categorical descriptive characteristics between groups	From chi-square tests (Pearson chi-square/Fisher exact test)
In comparing variables in groups according to follow-up times	Mixed order analysis of variance (ANOVA)
In comparing main effects in analyses	Bonferroni correction
Reliability for scales and their sub-dimensions	Cronbach's Alpha coefficient
In evaluating missing data	intention to treat (ITT) analysis

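### The 95% power is correctly computed for a Mann-Whitney test the SAP does not run; it is not shown for the mixed ANOVA, and the second primary outcome has no power calculation

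*Protocol*

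**What the plan says.** Protocol section 1.3 takes its effect size from one earlier study of "treatment compliance in patients with hypertension, was used for the calculation". It sets "the alpha value of 0.05 for the Mann Whitney U test, the effect size of 0.90, and the theoretical power as 95"% and arrives at "35 people for the control group + 35 people for the experimental group; 70 people in total". A 10% loss allowance raises this to 39 per arm, 78 in all. The protocol's Abstract then attaches the figure to the randomised number: "39 in the intervention group and 39 in the control group, calculated with 95% power".

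Section 1.9.8 names two primary outcomes: "The primary outcomes of this study were the level of compliance with antihypertensive drug treatment and healthy lifestyle behaviors". Both are measured at T0, T1 and T2.

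The SAP lists no Mann-Whitney test. Its t test and chi-square tests are for descriptive characteristics. For the outcomes, "Mixed order analysis of variance (ANOVA) was used to compare variables according to follow-up times in groups". The analysis set is n = 78, and for the seven leavers "the post-tests were filled in by repeating the answers given by the patients in the pre-tests". The SAP does not say which ANOVA term tests the intervention. It mentions only main effects, in the line on the Bonferroni correction. The group-by-time effect is mentioned in protocol section 1.13 (Limitations).

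**The concern.** The calculation behind the 95% and the analysis differ in three respects.

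- **Test.** The calculation is a two-group comparison at one time. The analysis is a 2x3 mixed ANOVA, whose terms have different power. The group main effect averages in T0, where randomisation makes the true difference zero.
- **Who is analysed.** The loss allowance treats leavers as gone, leaving 35 completers. The analysis keeps them, with their T0 values as T1 and T2, so they contribute no treatment effect.
- **Outcomes.** The effect size is for treatment compliance. HLBS-II is also primary and has no calculation.

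At stake is a public design claim. A reader of the Abstract will take 95% as the power of the reported analysis of 78 participants, for both primary outcomes. Someone reusing the design would inherit that assumption.

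**Working it through.** **Inputs from the documents.** Alpha 0.05, effect size 0.90 (read as Cohen's d), 95% power, 35 then 39 per arm, 10% loss (protocol 1.3); 3 intervention and 4 control leavers (protocol 1.7); baseline carried forward, n = 78 (SAP).

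**Assumptions, because the documents are silent.** Two-sided test (this reproduces 35; one-sided gives 29). Normal data, SD 1, equal correlation r between visits, r = 0.3 to 0.7. Effect 0.90 at T2 in those who stay, with either the full or half the effect at T1. Leavers: 3 and 4 as observed, or 4 and 4 as the 10% allowance implies.

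**1. The plan's own figure.** With Mann-Whitney efficiency 3/π, the effective n per arm is m = n × 3/π, df = 2m − 2, and the noncentrality is λ = d√(m/2).

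- n = 35: m = 33.42, λ = 0.90 × √16.71 = 3.68, power 95.2%.
- n = 34: power 94.6%, so 35 is the smallest n that suffices.
- 35/0.90 = 38.9, rounded up to 39; 70/0.90 = 77.8, rounded up to 78.

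The stated figure reproduces. With 39 per arm and no loss it would be 96.9%.

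**2. Effect of carrying T0 forward.** Intervention leavers show no effect, so the mean difference shrinks to 0.90 × 36/39 = 0.83 (3 leavers) or 0.90 × 35/39 = 0.81 (4 leavers). For a Mann-Whitney test at T2 with 39 per arm, m = 37.24:

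- d = 0.83: λ = 0.83 × √18.62 = 3.58, power 94%.
- d = 0.81: λ = 0.81 × √18.62 ≈ 3.49, power 93%.

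Analysing 39 rather than 35 offsets most of the dilution; the cost is about 0 to 3 points.

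**3. Why the ANOVA term matters.** Before dilution, the group effect averaged over three visits is (0 + 0.90 + 0.90)/3 = 0.60, or (0 + 0.45 + 0.90)/3 = 0.45 with half the effect at T1. The SD of a person's three-visit mean is √((1 + 2r)/3): 0.730 at r = 0.3 and 0.894 at r = 0.7. The standardised main effect is therefore 0.60/0.730 = 0.82 down to 0.60/0.894 = 0.67 (full), or 0.45/0.730 = 0.62 down to 0.45/0.894 = 0.50 (half). All are below 0.90. Group-by-time moves the other way and gains power as r rises.

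**4. Simulated power, %** (39 per arm, 6,000 runs per setting, standard error at most √(0.25/6000) = 0.65 points; each cell shows 3/4 leavers, then 4/4).

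| r | Effect at T1 | Group-by-time | Group main effect | T2 t test, unadjusted |
|---|---|---|---|---|
| 0.3 | full | 93.0; 90.5 | 88.1; 85.6 | 95.1; 93.3 |
| 0.3 | half | 82.7; 80.2 | 66.4; 63.4 | 94.6; 93.6 |
| 0.5 | full | 98.0; 97.7 | 81.8; 79.3 | 95.0; 93.4 |
| 0.5 | half | 93.1; 93.2 | 58.0; 55.6 | 95.0; 93.7 |
| 0.7 | full | >99.9; >99.9 | 75.6; 72.6 | 95.0; 93.8 |
| 0.7 | half | 99.7; 99.4 | 51.1; 49.5 | 95.1; 93.8 |

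Repeat runs differ by about a point. The Mann-Whitney version of the T2 contrast is about 1 point lower than the t test. The rounded ranges are therefore 80% to over 99%, 49% to 89%, and 92% to 95%.

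**5. T2 adjusted for T0, same patients and carry-forward rule.** About 96% to 97% at r = 0.3, 99% at r = 0.5, over 99% at r = 0.7.

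**6. Is low r plausible for adherence?** Protocol 1.9.3 reports Cronbach's alpha of 0.674 at T0 and 0.748 at T2. Taken as rough reliabilities, they cap the observed correlation near √(0.674 × 0.748) = 0.71. A true correlation of 0.5 would then appear as about 0.5 × 0.71 = 0.36. Admitting only scores of 8 and above on a 1 to 13 scale would usually lower it further. This is indirect evidence; r itself is not reported.

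**The case against.** The strongest reply is that nothing is miscalculated and the trial may well have its 95%. Section 1.13 of the protocol rests its conclusion on group-by-time. With the observed losses, that test reaches 95% once r is about 0.4 (full effect at T1) or about 0.6 (effect building up). The weakest figures belong to the group main effect, which neither document names as the key test; a Bonferroni correction for comparing main effects does not make it so. The carry-forward rule costs little. The Abstract reports significant differences on adherence, lifestyle and blood pressure, so there is no null primary result to over-read.

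All of that stands, and it rules out the stronger inferences a reader might draw:

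- That the planned analysis fails to deliver 95%. The group-by-time range straddles 95%, and the documents fix neither the correlation nor the shape of the effect.
- That the sample size arithmetic is wrong. It is not.
- That power should be quoted at a halved alpha because there are two primary outcomes. Neither document splits alpha.

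The mismatch itself is unanswered. The Abstract's 95% is for a test that was not planned, the SAP does not name the ANOVA term, and HLBS-II has no calculation. It is also fair to object that an analysis added now is chosen with results known, and the fix has to say so.

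**Conclusion.** This is a mismatch between the power calculation and the analysis. The 95% is valid for a two-sided Mann-Whitney test of treatment compliance in 35 completers per arm at d = 0.90. For the mixed ANOVA of 39 per arm with T0 copied forward, it is not shown. Whether it is met depends on the ANOVA term, the correlation and the course of the effect, none of which the sample size section settles. The ranges above rest on normal data, d = 0.90 in those who stay, r between 0.3 and 0.7, and 3 to 4 leavers per arm; the documents do not allow 0.90 itself to be checked. Power for HLBS-II is unknown. The correction is worth making because it concerns a stated property of the design; it does not overturn the reported results.

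**What to change.** **Protocol, Abstract and section 1.3.** State that 95% refers to a Mann-Whitney test of adherence in 35 completers per arm. State that power for the mixed ANOVA was not calculated in advance, and give the range above with its assumptions. State that no power calculation was made for HLBS-II.

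**SAP.** Name group-by-time, rather than the group main effect, as the ANOVA test of the intervention. Add the between-group difference in adherence at T2, adjusted for the T0 score. Label it post hoc, because the SAP is dated June 2024, after T2 collection in May 2024, and the outcome results are already reported.

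**Cost.** Some rewording, one extra model on data already collected, and a less favourable power statement. No further patients are needed.

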#### **1.4. Inclusion and Exclusion Criteria for Participants in the Study**

In this study, the characteristics in Table 3.1 regarding the inclusion and exclusion criteria in the study group were taken into consideration.

**Table 1. Participant inclusion and exclusion criteria**

Inclusion	Exclusion

 
• Participants diagnosed with primary hypertension (at least one year)
 
• Between the ages of 40 and 59 *
 
• Those who use a mobile phone to receive the SMS to be sent by the researcher
 
• Those who are at least literate and can speak Turkish
 
• Those who have no communication problems in terms of hearing, seeing and understanding
 
• Those who use antihypertensive medication and who score “8 and above” on the compliance scale, and who are defined as non-compliant with treatment, were decided to be included in the study
 
	
 
• Those with a second chronic disease
 
• Those with a mental or communication problem
 
• Those with secondary hypertension (Addison's disease, Renal artery stenosis, Hypo/hyperthyroidism, Parenchymal kidney disease, Cushing's disease)
 
• Those who are pregnant or breastfeeding,
 

\* It is known that hypertension increases with age (Turkish Society of Endocrinology and Metabolism, 2022). At the same time, according to the socio-demographic data obtained from the ASM where the study was planned to be conducted, the age of the hypertensive individuals who will participate in the study is similar in terms of age, 40 and above, so the lower age limit was determined as 40 in our study. In addition, according to TÜİK data, the upper age limit was determined as 59 years due to the decrease in the rate of internet and mobile phone use in people over 60 years of age in our country (TÜİK, 2022).

[figure not shown]
#### **1.5. Exclusion Criteria from the Study**

1. Wanting to leave the study
2. Moving to another city during the follow-up period
3. Death during the follow-up period
4. Having acute health problems that require hospital monitoring and treatment during the follow-up period

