## 1.7. Reasons for Leaving the Study

The study started with a total of 78 participants and ended with “three” from the intervention group and “four” from the control group. After the participants left, the study was completed with a total of 71 patients, 36 from the intervention group and 35 from the control group. The patients who left the study stated the following reasons for leaving the study: “I am very busy, I can no longer spare time for your work” (n=3), “My blood pressure is no longer high, I am better, I want to leave your intervention” (n=1), “I cannot walk or diet, I cannot lose weight, I do not want to fill out your survey” (n=1) (5 patients in total). In addition, a total of 2 patients had to be removed from the study because the phone numbers they provided could not be reached by the researcher.

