Since the aim of the nursing profession is to produce information related to real-world practice beyond the boundaries of the laboratory, it is stated that the action approach will more accurately reflect nursing practice, however, it is said that blinding in action (pragmatic) experiments can generally be difficult (ethical, practical, etc. reasons) and sometimes even impossible, and in this case, it can be recommended to blind only those who evaluate the outputs and perform data analysis (Akın and Koçoğlu, 2017). For this purpose, in order to prevent bias in the evaluation of the data; statistical analyses of the coded data (A and B) in the prepared database were performed by a statistician, independent of the researcher. After the statistical analyses of the study and the appropriate tables for the results were made and the research report was written, the codings made for the control and intervention groups were explained. Thus, statistician and reporting blinding was performed during the research process. Intention to treat analysis (ITT) was applied to prevent attrition bias due to missing data in the outcome/outcome measurements during the study process after randomization. In this way, selection, attrition, statistical and reporting bias were controlled.

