### **1.14. Strengths of the Research**

- The results of this research have shown that remote health services can be provided to hypertensive individuals via mobile phones, and in this respect, it has contributed to the literature on the use of digital health technologies.
- It is thought that the research will contribute to evidence-based nursing due to the fact that the research was conducted in a randomized controlled manner, blind technique was used, and ITT analysis included effect size and confidence intervals.
- The fact that the nursing interventions (SMS message and education) applied in the research were free, easy and simple shows that they are feasible in terms of cost.
- In addition, the use of theory in the foundation of nursing interventions in this research is one of the strengths of the research.

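### The only planned analysis counts all seven leavers as unchanged from pre-test; an analysis of the observed values is needed beside it

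*Protocol*

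**What the plan says.** Protocol section 1.7 reports that 78 participants started and 71 completed, 36 in the intervention arm and 35 in the control arm. Five of the 7 leavers gave a reason of their own. One said "My blood pressure is no longer high, I am better, I want to leave your intervention"; another ended with "I do not want to fill out your survey". The other two "had to be removed from the study because the phone numbers they provided could not be reached".

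Protocol section 1.15 and the SAP give the same missing-data procedure: for these 7, post-test values repeat the pre-test answers. Both call this intention to treat. The SAP's Table 1 is headed n=78, and intention to treat is its only missing-data entry. Neither document names an observed-data, completer, mixed-model or imputation analysis as a check.

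Two statements rest on this procedure. Section 1.8 says of it: "In this way, selection, attrition, statistical and reporting bias were controlled". Section 1.14 lists among the strengths that "ITT analysis included effect size and confidence intervals".

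Section 1.5 lists four grounds for exclusion during follow-up: wish to leave, death, "Moving to another city during the follow-up period" and "Having acute health problems that require hospital monitoring and treatment during the follow-up period". It does not say whether outcomes are still sought after such an event.

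**The concern.** Keeping all 78 in the table preserves the randomised groups in form. It does not supply the missing outcomes. Copying the pre-test forward asserts that each leaver stayed exactly where they began, and it does so without any uncertainty. Two things follow. Each arm mean is pulled towards its own baseline by the share filled in that arm, and the shares differ. The invented values also enter the sample size and the variance as if measured, so the confidence interval is narrower than the observed data justify.

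The effect size and the interval are what section 1.14 puts forward as a strength. With no second analysis, a reader cannot see how far they depend on the zero-change assumption, and the statement that attrition bias was controlled goes further than the method can support.

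**Working it through.** **Inputs.** Section 1.3: 35 per group required (alpha 0.05, effect size 0.90, power 95%, Mann-Whitney U); loss allowance from "The 10% loss rate in previous studies"; 39 per group planned. Section 1.7: 36 and 35 completers. The documents give no outcome means or SDs, so everything from step 4 on is illustration.

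**1. The plan's own figure.** With the noncentral t distribution, Mann-Whitney efficiency 3/π, two-sided alpha 0.05 (sidedness is not stated) and d = 0.90, 35 per group gives power 0.952. Then 35/0.90 = 38.9, rounded up to 39. The sample size reproduces.

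**2. Share filled.**
- Intervention: 3/39 = 7.7%
- Control: 4/39 = 10.3%
- Total: 7/78 = 9.0%, within the planned 10%. The reasons add up: 3 + 1 + 1 + 2 = 7 = 78 − 71.

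The 36 and 35 completers meet the 35 required. Mann-Whitney power at d = 0.90 with 36 v 35 is 95.5%, so sample size is not the problem and an analysis without filling was affordable.

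**3. Weight of the assumption.** For each point by which the leavers' true mean change differs from zero, the arm mean is off by 3/39 = 0.077 (intervention) or 4/39 = 0.103 (control) points.

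**4. Effect on the contrast.** Let dI and dC be the completers' mean changes, and assume that leavers would have changed like completers of their arm.

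Filled contrast = (36·dI − 35·dC)/39

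Filled minus unfilled = (4·dC − 3·dI)/39

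With dC = c·dI, this difference is zero at c = 3/4.

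| c | Filled (× dI) | Unfilled (× dI) | Difference |
|---|---|---|---|
| −1 | 71/39 = 1.821 | 2 | −9.0% |
| 0 | 36/39 = 0.923 | 1 | −7.7% |
| 0.5 | 18.5/39 = 0.474 | 0.5 | −5.1% |
| 0.75 | 9.75/39 = 0.250 | 0.25 | 0 |
| 0.9 | 4.5/39 = 0.115 | 0.1 | +15% |

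Below 75% the filling shrinks the contrast. Above it, the filling moves the contrast in favour of the intervention.

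**5. Estimate, interval and test at the planned effect.** Further assumptions: 0.90 is in SDs of change, dC = 0, one change score, two-sample t test, 40,000 simulated trials.

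| | Estimate (SD) | Mean 95% CI width | Power |
|---|---|---|---|
| Observed, 36 v 35 | 0.90 | 0.943 | 0.961 |
| Filled, 39 v 39 | 0.83 | 0.871 | 0.964 |

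The interval narrows by 1 − 0.871/0.943 = 7.6%, almost the same proportion as the estimate (7.7%). Their ratio hardly moves, which is why power does not change.

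**6. If the effect size is standardised by the filled data's own SD.** The expected within-arm sums of squares are 35 + (36·3/39)(0.81 + 1/36) = 37.32 and 34 + (35·4/39)(1/35) = 34.10. The pooled variance is (37.32 + 34.10)/76 = 0.940, so the SD is 0.969. Then 0.831/0.969 = 0.857 against 0.90, about 5% lower rather than 7.7%. The documents do not say which effect size was used.

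**The case against.** The strongest case against is that the effect is small. Loss was within plan, and under the illustrative assumption the test result barely moves. The simulation is also simpler than the planned three-time mixed ANOVA. A mixed model assumes data missing at random, and if the leavers gave only T0 values it comes close to a completer analysis. It would not probe dropout that depends on the unseen outcome. All of this stands. It limits the point to the effect size, the interval and the claim of control; it does not remove the need to show a result free of invented values.

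A reader might infer more, in four ways that the documents do not support.

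- **That section 1.5 biased the results by discarding participants who moved or were hospitalised.** Section 1.7 reports no such loss. Whether the two unreachable participants had moved cannot be told; their removal can be read as ordinary loss to follow-up, and nothing shows that their outcomes were obtainable. That a participant excluded under 1.5 would be filled in the same way is also an inference, because the filling text concerns the 7 who left.
- **That the SAP contradicts itself by describing last observation carried forward and then using pre-test answers.** The two agree if all 7 left before T1. The flow chart that may show this is not available here.
- **That the leaver who felt better proves that an improvement was hidden.** The remark is translated and comes without a measurement, arm or date. It shows only that no change is an assumption.
- **That the filling is safely conservative.** Step 4 shows it can favour the intervention, and if leavers worsened it flatters their arm.

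**Conclusion.** The point holds for the missing-data analysis. For 9.0% of participants the outcome change is set to zero and treated as observed, this is the only analysis named, and sections 1.8 and 1.14 claim more for it than it can deliver. If leavers resembled completers, control did not change and the effect was the planned 0.90 SD, the estimate would be 0.83 SD and the interval about 7.6% too narrow, with the significance test essentially unaffected. Those figures rest on assumptions. The actual size and direction cannot be computed from the documents, and nothing here shows that the reported conclusions are wrong. The text speaks of copied answers, so its application to blood pressure is likely but not explicit.

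The silence of section 1.5 on outcome collection after a move or hospital care is a drafting gap that matters only if the protocol is reused. It did not affect the present results as reported.

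**What to change.** 1. **For the completed trial.** Fit a likelihood-based mixed model (arm, time, arm × time) to the observed T0, T1 and T2 values, with no pre-test filling and keeping any T1 value that a leaver gave. Report its effect size and 95% confidence interval beside the filled ones, name the effect-size definition, and say whether the conclusions hold.
2. **Wording.** Limit the section 1.8 statement on attrition bias to what the two analyses show together. State when each of the 7 left and whether the filling was also applied to blood pressure.
3. **For reuse of the protocol only.** Have section 1.5 separate the end of the intervention from the end of outcome collection, and say how outcomes are sought after a move or hospital care, by the same contact rule in both arms. This concerns data collection, not care.

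**Cost.** Items 1 and 2 need one extra analysis of data already held and a few sentences. The model assumes missing at random and adds little beyond a completer analysis if leavers gave only T0 values. Item 3 would mean some contact attempts and some questionnaires by telephone or outside the visit window, whereas the design collects them face to face; blood pressure might still be missing.
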